8.5. Completion of the Trial

The trial will be considered to have been completed upon the last visit of the last patient who had their treatment extended to Week 98.

8.6. Patient Withdrawal Criteria

Any patient can decide to withdraw from study participation at any time for any reason. A patient who discontinues may be replaced at the discretion of the Sponsor. In addition, the study Sponsor may decide to stop the study participation of any patient as deemed necessary. The Investigator may also stop the study participation of any patient at any time. Reasons for withdrawal from the study include, but are not limited to:

- The patient was erroneously included in the study (ie, was found to not have met the eligibility criteria).
- The patient experiences an intolerable or unacceptable AE.
- The patient is unable to comply with the requirements of the protocol.
- The patient participates in another investigational study without the prior written authorization of the Sponsor.

The Investigator or study staff will document the reason(s) for treatment discontinuation.

Patients who have received at least 1 dose of study treatment and who are withdrawn from treatment within 28 days after a functional assessment visit will be asked to return for an Early Termination visit (to complete the Week 96 assessments) approximately 28 days after their last dose. Patients who receive at least 1 dose of study treatment who are withdrawn from treatment more than 28 days after a functional assessment visit will be asked to complete all early termination (Week 96) assessments within approximately 28 days after the last dose.

Patients withdrawn from treatment will not be replaced.

8.7. Study Discontinuation

If the Sponsor, the Investigator, the Medical Monitor, the study monitor, IRB/IEC, or appropriate regulatory officials discover conditions arising during the study that indicate the study should be halted or that the study center should be terminated, appropriate action may be taken after consultation among (at a minimum) the Sponsor, the Investigator, the IRB/IEC, and the Medical Monitor.

Conditions that may warrant termination of the study or an individual site include, but are not limited to, the following:

- The discovery of an unexpected, serious, or unacceptable risk to patients enrolled in the study
- A decision by the Sponsor to suspend or discontinue testing, evaluation, or development of the product
- Failure of the Investigator to enroll patients into the study at an acceptable rate

- Failure of the Investigator to comply with pertinent regulations of IRB/IEC or appropriate regulatory authorities
- Failure of the Investigator to comply with the protocol
- Submission of knowingly false information from the research facility to the Sponsor, the study monitor, IRB/IEC or regulatory authority
- Insufficient adherence to protocol requirements consistent with the European Clinical Trial Directive 2001/20/EC

9. TREATMENT OF PATIENTS

9.1. Investigational Product

Eteplirsen drug product is supplied as a sterile, phosphate-buffered saline solution in single-use, 2-mL vials each containing 2 mL of eteplirsen at 50 mg/mL. The solution is a clear to slightly opalescent and colorless liquid that may contain white to off white particles. Eteplirsen will be administered once a week by IV infusion.

9.1.1. Packaging and Labeling

Please refer to the study-specific Pharmacy Manual for information on packaging, labeling, and preparation instructions.

The label text for the IP will at a minimum include the following information: product name/identifier, cautionary statement, lot number (or alternative code), storage conditions, and the name of the Sponsor pursuant to regional requirements.

9.1.2. Storage

Vials of IP must be stored in a secured, limited access area with appropriate temperature recording, controls, and monitoring. Details for storage can be found in the study-specific Pharmacy Manual.

9.2. Treatments Administered

Eligible patients will receive a once weekly IV infusion of eteplirsen for up to 96 weeks. Eteplirsen should be prepared for dosing by following the steps detailed in the study-specific Pharmacy Manual.

The starting dose is 2 mg/kg eteplirsen, with escalation to 4, 10, 20, and 30 mg/kg over the course of the dose-titration period.

The following guidelines for the timing of dosing should be followed throughout the study:

- Patients should receive Eteplirsen once every 7 days starting on Week 1. A window of ± 3 days from the scheduled dose is acceptable after the first infusion.
- Patients may not receive 2 separate doses of Eteplirsen within the same 60-hour period.
- The Medical Monitor should be contacted in the event of ≥2 consecutive missed doses.

The administered dose is calculated by patient weight, which will be collected on a weekly basis and used to calculate the dose to be administered at the next visit(s). For example, the weight collected at Week 2 will be used to calculate the doses to be infused during the Week 3 visit.

Eteplirsen should be diluted in a normal saline, where the final volume, after eteplirsen has been added, equals the volume appropriate for the patient's weight. The drug delivery bag, syringe or flask is to be labeled in accordance with standard pharmacy practice and to include total volume as well as drug dose in milligrams. Eteplirsen will be diluted in normal saline to a total volume per Table 5 and infused IV for approximately 35 to 60 minutes using an infusion or syringe

pump. It is recommended that a topical anesthetic cream be applied to the infusion site prior to each administration of eteplirsen.

Table 5: Example Eteplirsen Dilution Scheme

Patient Weight	Total Eteplirsen Dose (30 mg/kg)	Total Volume of Eteplirsen Drug Product	Dilution in Saline up to Total Volume of:	Maximum Eteplirsen Concentration in Infusion
<5 kg	<150 mg	<3 mL	10 mL	15 mg/mL
5 to 10 kg	150 to 300 mg	3 to 6 mL	15 mL	20 mg/mL
10 to 15 kg	300 to 450 mg	6 to 9 mL	25 mL	18 mg/mL
15 to 25 kg	450 to 750 mg	9 to 15 mL	50 mL	15 mg/mL
>25 kg	>750 mg	>15 mL	100 mL	

Note: Refer to the Pharmacy Manual for other dosing dilution schemes.

An implanted venous access port may be inserted for eteplirsen administration at the discretion of the Investigator. If eteplirsen is administered into an existing IV line, the line should be flushed with normal saline before and after administration of eteplirsen. After eteplirsen administration and the saline flush, the port may be flushed with heparin to heplock the port prior to removal of the infusion line.

No other medications may be administered concomitantly during the eteplirsen infusion. Patients are permitted to continue a chronic, stable regimen of corticosteroids; however, the corticosteroid should not be administered during the infusion of eteplirsen.

All treated patients will be observed for at least 1 hour following the end of each eteplirsen infusion.

9.2.1. Dose Modification, Reduction, or Delay

9.2.1.1. Dose Interruption

The following rules apply to individual dosing interruption, ie, the criteria for dosing interruption of 1 patient. Further administration of eteplirsen must be discontinued if any of the following occur:

[figure not shown]
- Any serious adverse event (SAE) considered to be related to eteplirsen, unless the SAE is deemed related to the underlying disease
- See Section Section 10.3.4 for Safety Monitoring, Additional Investigations and Stopping Rules

If a patient meets one of the above criteria or under Section 10.3.4, the study monitor should be immediately notified, and dosing should be suspended until the patient's safety information can be reviewed by the DMC. Dosing may resume only after approval of the DMC, Sponsor, and Investigator, and after approval of a substantial amendment by the competent authority.

Conditions that may warrant interrupting dosing for all patients in the study for additional safety review include, but are not limited to:

- Any SAE of life-threatening or fatal outcome assessed as related by the Investigator
- > 2 patients with severe AEs that result in interruption of individual patient dosing (described earlier in Section 10.3.4)
- Any unexplained or drug-related organ failure (eg, liver or renal failure)

The DMC will monitor safety data on an ongoing basis. If the DMC determines that the criteria for study interruption are met, dosing will be suspended until all available patient information related to the event of interest can be reviewed in more detail. Discontinuation of dosing for an individual patient may occur based on the recommendation of the DMC, investigator, the patient, and the local Independent Ethics Committee (IRB/IEC).

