10.3.4. Safety Monitoring, Additional Investigations and Stopping Rules

10.3.4.1. Safety Monitoring for Liver Chemistry Tests

Liver chemistry tests need to be monitored as specified in the Schedule of Events (Table 2). Initial abnormal liver chemistry test result(s) needs to be confirmed if:

• Gamma-glutamyl transferase (GGT) or glutamate dehydrogenase (GLDH) or Aspartate aminotransferase (AST) or Alanine aminotransferase (ALT) measurement is > 3 x the upper limit of normal (ULN) (or > 2 x Baseline value if the Baseline value was > ULN) at any time during the study.

Patients with confirmed liver chemistry test results (as above) need to have their liver chemistry tests (GGT, GLDH, ALT, AST, alkaline phosphatase (ALP), international normalized ratio (INR) and total bilirubin) retested two or three times weekly. Frequency of retesting can decrease to once a week or less if abnormalities stabilize or the trial drug has been discontinued and the subject is asymptomatic.

Additional Investigations:

Patients with confirmed abnormal liver chemistry test results (as above) are recommended to have the following evaluations performed:

- Obtaining a more detailed history of symptoms and prior or concurrent diseases.
- Obtaining a history of concomitant drug use (including nonprescription medications and herbal and dietary supplement preparations), alcohol use, recreational drug use, and special diets.
- Ruling out acute viral hepatitis types A, B, C, D, and E; autoimmune or alcoholic hepatitis; Non-Alcoholic SteatoHepatitis; hypoxic/ischemic hepatopathy; and biliary tract disease.
- Obtaining a history of exposure to environmental chemical agents.
- Additional liver evaluations, including gastroenterology/hepatology consultations, hepatic computed tomography (CT) or magnetic resonance imaging (MRI) scans, may be performed at the discretion of the Investigator, in consultation with the Sponsor Medical Monitor.

Stopping Rules for Liver Test Results:

In the event of laboratory results meeting the following criteria, and the event is without an alternative explanation as discussed with the Sponsor Medical Monitor, dosing of a patient with eteplirsen will be stopped permanently; values that are not confirmed due to failure to retest or missing lab values will be presumed confirmed:

- GGT or GLDH > 8 x ULN, which is confirmed
- GGT or GLDH > 5 x ULN, which is confirmed and persists for ≥ 2 weeks

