In the event of a confirmed hypersensitivity AE meeting the following criteria, and the event is without an alternative explanation as discussed with the Sponsor Medical Monitor, dosing of a patient with eteplirsen will have their treatment permanently discontinued.

- Anaphylaxis, anaphylactoid reaction, or angioedema
- Any serious allergic reaction

Safety Monitoring for Platelet Count Results

The platelet count needs to be monitored as specified in the Schedule of Events (Table 2).

Patients who have a confirmed occurrence of platelets < 75,000/ mm³ need to have the following evaluations performed:

- Complete blood count (CBC) with reticulocytes
 - Peripheral blood smear
 - Coagulation panel (prothrombin time /INR, activated partial thromboplastin time)
 - High-sensitivity C-reactive protein

Additional Investigations:

Additional platelet evaluations for confirmed, unexplained significant platelet count reductions, including hematology consultation, fibrinogen, fibrinogen split products/D-dimer, von Willebrand factor, total immunoglobulins, complement levels, viral serologies, auto-antibody screen, antiplatelet antibodies and anti-PF4 assay, may be performed at the discretion of the Investigator in consultation with the Sponsor Medical Monitor.

Stopping Rules for Platelet Test Results:

In the event of laboratory results meeting the following criteria, and the event is without an alternative explanation as discussed with the Sponsor Medical Monitor, dosing of a patient with eteplirsen will be stopped permanently:

• Platelet count < 50,000/mm³

Safety Monitoring for Rhabdomyolysis

Rhabdomyolysis must be monitored by urine dipstick and adverse events as specified in the Schedule of Events (Table 2).

Patients who have confirmed heme+ dipstick urinalysis need to be evaluated for urine microscopy and the following AEs:

Rhabdomyolysis

- Acute onset or exacerbation of Myalgia
- Myoglobinuria
- Chromaturia (eg, tea-colored urine)

Additional Investigations:

In case of any of the adverse events above, subjects need to have evaluations of myoglobinuria, creatine kinase (CK), renal function (eg, serum cystatin C) and serum chemistry two or three times weekly until values reach usual/pre-event levels or stabilize.

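### Protocol Sections 9.2.1.1 and 10.3.4 contradict each other on whether dosing stopped under a Section 10.3.4 stopping rule can ever resume, and on who decides

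*Protocol*

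**What the plan says.** Section 9.2.1.1 (Dose Interruption) sets the rules for a single patient. It opens with "Further administration of eteplirsen must be discontinued if any of the following occur" and lists related serious adverse events, then sends the reader to Section 10.3.4 "for Safety Monitoring, Additional Investigations and Stopping Rules". The procedure follows, and it expressly takes in patients who qualify through the later section: "If a patient meets one of the above criteria or under Section 10.3.4, the study monitor should be immediately notified". What then happens to treatment is described as a hold, not an end: "dosing should be suspended until the patient's safety information can be reviewed by the DMC". The route back is in the next sentence: "Dosing may resume only after approval of the DMC, Sponsor, and Investigator, and after approval of a substantial amendment by the competent authority".

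Section 10.3.4 states what happens when a stopping criterion is met and discussion with the Sponsor Medical Monitor yields no alternative explanation. For liver, renal and platelet criteria, "dosing of a patient with eteplirsen will be stopped permanently". For hypersensitivity, "dosing of a patient with eteplirsen will have their treatment permanently discontinued". It mentions no DMC review and no resumption, and it does not refer back to 9.2.1.1.

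Two further statements in 9.2.1.1 bear on the point. The study-level trigger based on more than 2 patients counts severe adverse events that led to interruption of a patient's dosing, and it cites Section 10.3.4 as the place where these are described. The closing sentence says that discontinuation of an individual patient is something that may happen on the recommendation of the DMC and others.

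**The concern.** These are the individual stopping rules in a study of children aged 6 to 48 months, an age group in which Section 5.4 says eteplirsen has not been studied before. Safety and tolerability are the primary endpoint. An investigator with a qualifying result needs to know whether the child is on hold or finished with treatment, and whose decision that is. A family needs the same answer. The DMC also needs to know whether a case stopped under 10.3.4 comes to it for a decision on resumption or is already closed.

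Read together, the two sections do not say. One treats a 10.3.4 event as a suspension that can be lifted, and the other treats it as final.

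**Working it through.** No arithmetic decides this point. The check is a comparison of the two sections on trigger, action, decision-maker and reversibility.

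| | Section 9.2.1.1 | Section 10.3.4 stopping rules |
|---|---|---|
| Trigger | Related serious adverse event, or any criterion under Section 10.3.4 | Listed liver, renal, hypersensitivity or platelet criterion |
| Condition | For the 10.3.4 criteria, none stated | No alternative explanation |
| Action | Opens with discontinuation, then suspension pending review | Permanent stop or permanent discontinuation |
| Who is involved | Study monitor notified; DMC reviews; DMC, Sponsor and Investigator approve; competent authority approves a substantial amendment | Discussion with the Sponsor Medical Monitor |
| Way back | Yes, under those approvals | None stated |

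**Step 1: do the triggers overlap?** Yes. The procedure in 9.2.1.1 begins "If a patient meets one of the above criteria or under Section 10.3.4", with no exception. The stopping rules in 10.3.4 comprise 4 liver, 5 renal, 2 hypersensitivity and 1 platelet criteria, and 4 + 5 + 2 + 1 = 12. Every one of them falls within those words.

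**Step 2: do the consequences agree?** No. Take a serious allergic reaction judged related to eteplirsen, with no alternative explanation. As a related serious adverse event and as a 10.3.4 criterion, it leads under 9.2.1.1 to suspension with possible resumption. Under the hypersensitivity rule in 10.3.4 it leads to permanent discontinuation. Both rules apply to the same child, and they differ on whether the stop can be reversed.

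**Step 3: does other text in 9.2.1.1 settle it?** No. The section begins with mandatory discontinuation, moves to suspension, and ends with discontinuation as a possibility. Its study-level trigger calls 10.3.4 outcomes interruptions, whereas 10.3.4 calls them permanent. The difference in terms therefore carries into the rule for pausing the whole study.

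**Step 4: which 10.3.4 criteria are meant?** This is not stated. Besides stopping rules, 10.3.4 holds thresholds that call only for repeat testing or further evaluation, such as KIM-1 or cystatin C above the upper limit of normal, or platelets below 75,000/mm³ (the platelet stopping rule is below 50,000/mm³). It also has a rhabdomyolysis subsection with no stopping rule. Taken literally, 9.2.1.1 could suspend dosing on any of these.

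**The case against.** The best defence reads the two sections as a sequence. Whether an alternative explanation exists cannot be known when the result arrives. On this reading 9.2.1.1 supplies the immediate step (notify, suspend, review), and 10.3.4 supplies the outcome once the cause has been considered. The resumption clause also has work to do elsewhere, since related serious adverse events outside the 10.3.4 rules carry no permanent-stop wording. This is a sensible reading, but the text does not state it. Section 9.2.1.1 does not confine resumption to patients with an alternative explanation, and it names different decision-makers from 10.3.4. For a child with no alternative explanation, the two rules still disagree.

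The second defence is that the clause restricts more than it permits. Resumption needs three approvals and an approved substantial amendment, and that amendment could itself change 10.3.4. This stands as far as it goes. Until an amendment is approved, both sections keep the child off drug. It does not settle whether the child's status meanwhile is suspended or permanently stopped, or who determines that.

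A reader might infer three stronger things that the documents do not support:

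- **Sites could restart children by different rules.** No site can resume dosing alone under either section.
- **One child classified differently moves a cohort's discontinuation rate by 1/6 = 16.7 percentage points, so the conflict has that size.** The arithmetic is true of any one-child event in a cohort of 6 and does not measure this conflict. The documents give no expected frequency for these events.
- **The SAP's count of adverse events leading to discontinuation (Section 6.8.1) will be wrong.** Action taken with study drug is recorded in the eCRF (protocol Section 11.3.6). The completion guidelines, which may settle the coding, were not available here.

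**Conclusion.** The contradiction is real and stands in the current protocol text. For all four families of stopping rule, Section 9.2.1.1 describes a stop that can be lifted and Section 10.3.4 describes one that cannot, with different people deciding. The scope of the reference to 10.3.4 is also unclear. The approval and amendment conditions limit the practical danger, since they make unreviewed re-dosing unlikely. It should still be corrected, because the individual safety rules ought to have one meaning.

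The conclusion rests on the visible text. An image directly above the list in 9.2.1.1 is not shown in the copy reviewed, so that list may not be complete. The DMC Charter was not available and may set out a sequence. If it does, the protocol should still say the same thing. No view is taken on which rule is clinically right.

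**What to change.** Reconcile Sections 9.2.1.1 and 10.3.4:

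- For each criterion, state once whether meeting it leads to suspension with possible resumption or to permanent discontinuation, what part an alternative explanation plays, and who decides. Have both sections refer to that statement.
- Say whether the reference to Section 10.3.4 in 9.2.1.1 means the stopping rules only or also the retest and evaluation thresholds.
- Word the study-level trigger based on more than 2 patients in the same terms, so that it is clear which individual outcomes count towards it.
- Align the opening and closing sentences of 9.2.1.1 with the result.

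Which consequence attaches to which criterion is for the sponsor and the DMC. The cost is a protocol amendment, which Section 14.2 makes subject to ethics and regulatory review. It requires no additional patients or data.

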9.2.1.2. Dose Escalation

Increases in dosing up to 30 mg/kg are described in Section 9.2.

9.3. Randomization and Blinding

This is an open-label study, and therefore all patients will receive eteplirsen.

9.4. Prior and Concomitant Medications

No other medications may be administered concomitantly during the eteplirsen infusion.

The following therapies are not permitted during the conduct of this study:

- Previous or current investigational agents (with the exception of drisapersen: patients may be included in the study if they have not received drisapersen for 6 months prior to the Week 1 dose)
- Immunosuppressants (other than oral or systemic corticosteroids; the corticosteroid should not be administered during the infusion of eteplirsen)
- Previous (within 12 weeks prior to the Week 1 dose) or current systemic aminoglycoside antibiotic or statin

In general, drug therapies that are not excluded per the entry criteria, including over-the-counter medications, may be used before enrollment and throughout the study. However, the number of over-the-counter medications should be limited and the dosage of any medication should be constant for at least 1 month prior to starting study treatment and throughout the study, especially during the dose-escalation period and throughout the first 6 months in the study, unless clinically indicated.

The Investigator should contact the Medical Monitor if he/she is unsure about changing a specific medication.

9.5. Treatment Compliance

Treatment compliance will be assessed via compliance with scheduled weekly infusions.

10. STUDY ASSESSMENTS

10.1. Study Schedule of Events

A detailed schedule of the study assessments and time points is shown in Table 2 and Table 3.

10.2. Screening/Baseline Assessments

10.2.1. Informed Consent

Written informed consent from the parent/legal guardian(s) to participate in this study must be obtained prior to beginning any of the procedures for this study.

